4 OBJECTIVES AND ENDPOINTS

Table 4-1: Objectives and Endpoints - Crohn’s Disease

Objective	Endpoint ^a
Primary	

 To assess the safety and tolerability of long-term use of deucravacitinib in participants with moderate to severe CD. 	
 Number and proportion of participants experiencing AEs, SAEs, AEs leading to study discontinuation, and AEs. Number and proportion of participants experiencing abnormalities in laboratory testing, ECG, and vital sign parameters over time. Changes from Day 1 for laboratory testing, ECG, and vital signs.
Exploratory	

[figure not shown]

Table 4-1: Objectives and Endpoints - Crohn’s Disease

Objective	Endpoint ^a
[Redacted Content]	

Abbreviations: AE = adverse event; AEI = adverse event of interest; CD = Crohn’s disease; ECG = electrocardiogram;

[Redacted Content] SAE = serious adverse event;

^a See [Section 10.4.1.1](#) for the definition of baseline for efficacy assessments.

Table 4-2: Objectives and Endpoints - Ulcerative Colitis

Objective	Endpoint ^a
[Redacted Content]	
Primary	

 To assess the safety and tolerability of long-term use of deucravacitinib in participants with moderate to severe UC. 	
 Number and proportion of participants experiencing AEs, SAEs, AEs leading to study discontinuation, and AEIs. Number and proportion of participants experiencing abnormalities in laboratory testing, ECG, and vital sign parameters over time. Changes from baseline for laboratory testing, ECG, and vital signs.
Exploratory	
[Redacted Content]	

Table 4-2: Objectives and Endpoints - Ulcerative Colitis

Objective	Endpoint ^a
[Redacted content]	

Abbreviations: AE = adverse event; AEI = adverse event of interest; ECG = electrocardiogram;

[Redacted content] SAE = serious adverse event; [Redacted content] UC = ulcerative colitis; [Redacted content]

^a See [Section 10.4.1.1](#) for the definition of baseline for efficacy assessments.

Table 4-3: Selected Endpoint Definitions

Endpoint	Definition
[Redacted content]	

Table 4-3: Selected Endpoint Definitions

Endpoint	Definition
[Redacted content]	

Table 4-3: Selected Endpoint Definitions

Endpoint	Definition
[Redacted]	
[Redacted]	[Redacted]
[Redacted]	[Redacted]
[Redacted]	[Redacted]
[Redacted]	[Redacted]
[Redacted]	[Redacted]
[Redacted]	[Redacted]

5 STUDY DESIGN

5.1 Overall Design

This is an open label, multi-center study to evaluate the long-term safety and tolerability of deucravacitinib in participants with moderate to severe CD or moderate to severe UC who have completed one of the applicable parent studies (IM011023, IM011024, or IM011127), are likely to safely derive a clinical benefit from ongoing treatment with deucravacitinib, and are willing and able to participate. Participants will receive deucravacitinib 6 mg BID PO in a tablet formulation.

[figure not shown]
The duration of the study is approximately 296 weeks (2,072 days) as follows:

- Qualification and enrollment: up to 28 days ([Section 5.1.2](#) [Treatment Period])

- Open-label study period: 288 weeks (2,017 days)
- Post-treatment follow-up period: 4 weeks (28 days; [Section 5.1.3](#) [Follow-up Period])

The study design schematic is presented in Figure 5.1-1.

Figure 5.1-1: Study Design Schematic

Abbreviations: BID = twice daily; BMS-986165 = deucravacitinib; DB = double-blind; EOT = end of treatment; F/U = follow-up; OLE = open-label extension; Q12W = every 12 weeks.

Physical exams, clinical laboratory evaluations, and other assessments, including the collection of blood [REDACTED] for [REDACTED] PK analysis, will be done at select visits during the study. Participants will be closely monitored for AEs throughout the study.

Blood samples will be collected prior to study treatment administration for PK analysis. Unscheduled visits will be allowed throughout the study period as needed for additional safety monitoring.

Throughout the study, participants who permanently discontinue study treatment prior to Week 288 are expected to be followed for protocol-specified follow-up procedures at the Final Safety Visit (4 weeks after the last dose of IP).

Blood samples will be collected prior to study treatment administration for PK analysis.

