^f Serum pregnancy test can be performed as an alternative to urine pregnancy test, based on the clinical judgment of the investigator. A serum pregnancy test should be performed prior to IP administration in WOCBP where a urine pregnancy test does not adequately exclude a clinical suspicion of pregnancy.

█ [REDACTED]

█ [REDACTED]

█ [REDACTED]

j On Day 1, after informed consent, study treatment should be taken from Study IM011077.

k Assessment will be performed during the PSEOT visit per protocol. Any missing data should be collected on Day 1.

Table 2-2: Year 1 Procedural Outline (IM011077) - Crohn's Disease

Procedure	Week 12 (Day 85)	Week 24 (Day 169)	Week 36 (Day 253)	Week 48 (Day 337) (or ET)	Final Safety Visit (28 days after ET)	Notes
Visit Window (\pm n days)	14	14	14	14	3	
Eligibility and Disease Assessments						
Tobacco/e-Cigarette Use	X	X	X	X	X	Section 6.3.2 (Tobacco and e-Cigarettes)
Concomitant Medication Use	X	X	X	X	X	Section 7.7 (Concomitant Therapy)
Physical Examination						
Physical Examination				X	X	Section 9.4.2 (Physical Examinations)
Targeted Physical Examination	X	X	X			Section 9.4.2 (Physical Examinations)
Vital Signs (heart rate, blood pressure, temperature)	X	X	X	X	X	Includes body temperature and seated blood pressure and heart rate. Blood pressure and heart rate should be measured after the participant has been resting quietly for at least 5 minutes.
Weight	X	X	X	X	X	
[REDACTED]						
ECG				X	X ^a	Section 9.4.4

Table 2-2: Year 1 Procedural Outline (IM011077) - Crohn’s Disease

Procedure	Week 12 (Day 85)	Week 24 (Day 169)	Week 36 (Day 253)	Week 48 (Day 337) (or ET)	Final Safety Visit (28 days after ET)	Notes
Blood, Urine, and Fecal Tests						
Hematology and Chemistry	X	X	X	X	X	Section 9.4.5 (Clinical Safety Labs)
Coagulation				X	X	
Fasting Lipid Panel and Glucose				X		Section 9.4.5 (Clinical Safety Labs)
Tuberculosis Risk Assessment				X		Appendix 5 (TB)
Urine Pregnancy Test ^d	X	X	X	X	X	Section 9.2.5 (Pregnancy); Section 9.4.5 (Clinical Safety Labs); Appendix 4
Urinalysis and Urine Chemistry	X			X	X	Section 9.4.5 (Clinical Safety Labs)
Pharmacokinetic Assessments	See Table 9.5-1 for sample collection details.					

Table 2-2: Year 1 Procedural Outline (IM011077) - Crohn’s Disease

Procedure	Week 12 (Day 85)	Week 24 (Day 169)	Week 36 (Day 253)	Week 48 (Day 337) (or ET)	Final Safety Visit (28 days after ET)	Notes
Endoscopy and Endoscopic Biopsies						

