Endoscopy (ileocolonoscopy) ^f				X		Section 9.1.1 (Endoscopies and Biopsies)
Additional Efficacy Assessments						
Health-Outcomes Assessments						

Table 2-2: Year 1 Procedural Outline (IM011077) - Crohn’s Disease

Procedure	Week 12 (Day 85)	Week 24 (Day 169)	Week 36 (Day 253)	Week 48 (Day 337) (or ET)	Final Safety Visit (28 days after ET)	Notes
Safety Assessment (in addition to the above)						
SAE Assessment	X	X	X	X	X	Section 9.2 (AEs); Appendix 3
AE Assessment	X	X	X	X	X	Section 9.2 (AEs); Appendix 3
Study Treatment						
Dispense Study Treatment	X	X	X	X ⁱ		deucravacitinib
Clinic Study Treatment Administration	X	X	X	X		Section 9.5 (Pharmacokinetics)
Review Study Treatment Compliance	X	X	X	X		Section 7.6 (Treatment Compliance)

Abbreviations: AE = adverse event; ECG = electrocardiogram; EOT = end of treatment; ET = early termination; FSH = follicle-stimulating hormone;

IRT = interactive response technology; n = number; SAE = serious adverse event; TB = tuberculosis; WOCBP = women of childbearing potential.

^a Required only if ECG at ET is abnormal.

^d Serum pregnancy test can be performed as an alternative to urine pregnancy test, based on the clinical judgment of the investigator. A serum pregnancy test should be performed prior to study treatment administration in WOCBP where a urine pregnancy test does not adequately exclude a clinical suspicion of pregnancy.

i [REDACTED]

f [REDACTED]

[REDACTED]

[REDACTED]

i Study treatment will not be dispensed at the EOT or ET visit.

General procedural note: The protocol does not mandate specific investigations at unscheduled visits. Unscheduled visit study procedures should be based on the clinical judgment of the investigator.

Table 2-3: Long-term Procedural Outline (IM011077) - Crohn’s Disease

Procedure		Q1	Q2	Q3	Q4	ET	Final Safety Visit (28 days after EOT or ET)	Notes
	Year 2	Week 60 (Day 421)	Week 72 (Day 505)	Week 84 (Day 589)	Week 96 (Day 673)			
	Year 3	Week 108 (Day 757)	Week 120 (Day 841)	Week 132 (Day 925)	Week 144 (Day 1,009)			
	Year 4	Week 156 (Day 1,093)	Week 168 (Day 1,177)	Week 180 (Day 1,261)	Week 192 (Day 1,345)			
	Year 5	Week 204 (Day 1,429)	Week 216 (Day 1,513)	Week 228 (Day 1,597)	Week 240 (Day 1,681)			
	Year 6	Week 252 (Day 1,765)	Week 264 (Day 1,849)	Week 276 (Day 1,933)	Week 288 (Day 2,017) EOT			
Visit Window (± n days)		14	14	14	14		3	
Disease Assessments								
Concomitant Medication Use		X	X	X	X		X	Section 7.7 (Concomitant Therapy)

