7.7.4.2 Corticosteroid Rescue Therapy and Tapering

[REDACTED]

[REDACTED] Failure to taper the corticosteroid dose to 0 mg daily [REDACTED] of initiation will be considered treatment failure, and participants must discontinue from the study, unless the participants require glucocorticoid treatment for adrenal insufficiency. Participants who remain on corticosteroids to treat adrenal insufficiency must be discussed with the BMS Medical Monitor/designee to continue the study. Rescue therapy with medications other than oral corticosteroids, including immunosuppressants or biologics for IBD, are not permitted.

Oral corticosteroid rescue therapy [REDACTED] may be used [REDACTED] in response to an increase in CD or UC disease activity at the investigator's discretion (refer to [REDACTED]). The oral corticosteroid should be tapered upon demonstrated disease improvement per investigator judgement. The recommended corticosteroid taper is as follows:

- [REDACTED]
- [REDACTED]
- [REDACTED]
- [REDACTED]

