8.1.2 Post Study Treatment Study Follow-up

Participants who discontinue study treatment will continue to be followed for 28 days post-last dose of study treatment, or longer, as required, and in line with [Section 9.2.3](#) (Follow-up of AEs and SAEs).

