All AEs (SAEs and nonserious AEs) for this study will be collected from the time the participant signs the informed consent form until the Final Safety Visit (ie, 28 days after EOT or ET) at the timepoints specified in [Section 2](#) (Schedule of Activities). All AEs reported during the parent study that have either resolved or are ongoing [REDACTED] after the PSEOT visit will be recorded as Medical History in Study IM011077. AEs that are ongoing from the parent study and worsen after the participant signs the informed consent form will be reported as new AEs in Study IM011077.

The investigator must report any SAE that occurs after these time periods and that is believed to be related to study treatment or protocol-specified procedure (eg, a follow-up skin biopsy).

- Medical occurrences that begin before the start of study treatment but after obtaining informed consent will be recorded on the appropriate section of the eCRF module.

- All SAEs will be recorded and reported to Sponsor or designee within 24 hours, as indicated in [Appendix 3](#).
- The investigator will submit any updated SAE data to the Sponsor or designee within 24 hours of updated information being available.

Investigators are not obligated to actively seek AEs or SAEs in former study participants. However, if the investigator learns of any SAE, including a death, at any time after a participant has been discharged from the study, and he/she considers the event reasonably related to the study treatment or study participation, the investigator must promptly notify the Sponsor.

The method of evaluating and assessing causality of AEs and SAEs and the procedures for completing and reporting/transmitting SAE reports are provided in [Appendix 3](#).

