10.4.2.1 Adverse Events

AEs for this study will be collected from the time the participant signs the informed consent form until the Final Safety Visit (ie, 28 days after EOT or ET) at the timepoints specified in [Section 2](#) (Schedule of Activities). AEs that are ongoing from parent studies that worsen after the participant signs the informed consent form will be reported as new AEs in Study IM011077. AEs reported during parent studies that have either resolved or are ongoing [REDACTED] from the parent study end of treatment visit will be recorded as Medical History in Study IM011077.

TEAEs are events that occur after the administration of the first dose of study treatment in Study IM011077. AEs that were ongoing during the parent study and worsen once study treatment is initiated in this study will also be considered treatment emergent. All AEs will be coded using the Medical Dictionary for Regulatory Activities (MedDRA) and presented by System Organ Class and Preferred Term. Serious AEs and deaths, AEs leading to study treatment discontinuation, AEs by maximum severity, and AEs by relationship will also be summarized by the MedDRA System Organ Class and Preferred Term. All TEAEs will also be summarized by Preferred Term sorted by decreasing frequency.

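### The Final Safety Visit is timed from last dose in Section 5.1 but from the EOT/ET visit elsewhere, and the TEAE definition has no end, so off-drug events count as treatment-emergent for a varying time in some early stoppers

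*Combined protocol and SAP*

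**What the plan says.** For participants who stop treatment before Week 288, Section 5.1 puts follow-up at the "Final Safety Visit (4 weeks after the last dose of IP").

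Sections 9.2.1 and 10.4.2.1 collect AEs from consent "until the Final Safety Visit (ie, 28 days after EOT or ET"). The schedules use the same kind of anchor: Tables 2-2 and 2-6 head the column "Final Safety Visit (28 days after ET"), and Tables 2-3 and 2-7 head it "Final Safety Visit (28 days after EOT or ET"), with a window of ±3 days. Schedule footnotes on dispensing treat EOT and ET as visits, not dosing dates. Section 5.1.2 requires an ET visit after permanent discontinuation but sets no maximum interval from last dose.

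Section 8.1.2 says that participants who stop "will continue to be followed for 28 days post-last dose of study treatment, or longer, as required".

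On classification, 10.4.2.1 says "TEAEs are events that occur after the administration of the first dose of study treatment in Study IM011077", and adds parent-study events that worsen once treatment starts. It gives no end. Section 9.2.1 also requires SAEs after the collection period to be reported if believed related, with no time limit.

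**The concern.** The numbers and proportions of participants with AEs, SAEs and AEs of interest are the primary endpoint (10.3.1). With no end in the TEAE rule, the only practical bound on off-drug events is the date collection stops, and the protocol fixes that date in two ways. Two participants who stop on the same day could have different off-drug windows because their ET visits were scheduled differently, or because their sites followed different sections.

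The off-drug period is not neutral. Section 7.4 has participants who need other rescue therapy stop study treatment in favour of an alternative, and 5.1.4 names biologics as an example. Infections and malignancies are events of interest (9.2.8). An infection that begins after such a switch would be tabulated as treatment-emergent on deucravacitinib. After collection ends, an SAE enters only if the investigator thinks it related, so the last part of the window is also selective.

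**Working it through.** **The plan's own figure.** The stated duration of about 296 weeks (2,072 days) includes the follow-up period: 4 + 288 + 4 = 296 weeks, and 296 × 7 = 2,072 days. The itemised days give 28 + 2,017 + 28 = 2,073; the one-day difference arises because Week 288 is Day 2,017 counted from Day 1. The figure reproduces. It does not settle the anchor, since 28 days of follow-up fits either reading.

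**Inputs from the documents.** Follow-up of 28 days; Final Safety Visit window of ±3 days; about 300 participants.

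**Not in the documents.** The gap g from last dose to the ET visit, the share who stop early, and event rates.

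**Off-drug days counted.**
- Last-dose anchor (5.1): 28 ± 3, that is 25 to 31 days.
- EOT/ET anchor (9.2.1, 10.4.2.1, Section 2): g + 28 ± 3 days.

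| Assumed g (days) | Last-dose anchor | EOT/ET anchor | Ratio of midpoints |
|---|---|---|---|
| 0 | 28 (25–31) | 28 (25–31) | 1.0 |
| 14 | 28 (25–31) | 42 (39–45) | 1.5 |
| 28 | 28 (25–31) | 56 (53–59) | 2.0 |
| 84 | 28 (25–31) | 112 (109–115) | 4.0 |

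If g exceeds 28 days, the Section 5.1 visit would fall before the ET visit, so the two texts could not both be followed.

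**Who is unaffected.** For completers, Table 9.5-1 has the Week 288 dose taken at the site and the schedules dispense nothing at EOT, so last dose and EOT visit coincide and g = 0. The same holds for a same-day ET visit.

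**Illustration of size (all rates assumed).** The chance that an early stopper has a first event of a given type in the extra g days is 1 − exp(−r × g/365.25). With r = 0.5 per person-year this is 1.9% at 14 days, 3.8% at 28 and 10.9% at 84. If 20% to 60% of 300 stop early (60 to 180 people), all with the same gap:
- g = 14: 1.1 to 3.4 participants
- g = 28: 2.3 to 6.8
- g = 84: 6.5 to 19.6

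At g = 28, varying r over 0.1, 1 and 2 gives 0.8%, 7.4% and 14.2% per early stopper. Because the endpoint counts participants, someone who already had the event on treatment adds nothing.

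**The case against.** The strongest reply is that the AE window itself is not contradictory. Sections 9.2.1 and 10.4.2.1 agree with each other, and Section 5.1 times a visit rather than AE collection. That is correct as far as it goes, but the window closes at the Final Safety Visit, so a different date for that visit is a different end of collection.

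A reader might also count 8.1.2 as a second conflict because it says "28 days post-last dose of study treatment". It does not conflict: the sentence continues by allowing longer follow-up, so it sets a minimum and needs only to be aligned.

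A reader might build a worst case from the visit spacing: 84 + 14 = 98 days off drug at a late ET visit and 98 + 28 + 3 = 129 at the Final Safety Visit. The documents do not support this as an expected delay. ET has its own column in Tables 2-3 and 2-7 with no window, it follows discontinuation, and unscheduled visits are allowed. Nor do they say that early stoppers are mainly treatment failures, or give any discontinuation rate.

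Section 7.7.4.2 says that failure to taper "will be considered treatment failure, and participants must discontinue from the study". One might infer that these participants get no follow-up. Sections 5.1.2, 5.1.3, 7.7.4.1 and 8.1 send those who stop study treatment into follow-up, so this is a wording conflict to reconcile, not evidence of missing data.

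Two further points stand in mitigation: counting extra off-drug events tends to overstate risk rather than hide it, and AEs are also summarised by relationship. Section 10.4.1 leaves analysis detail to the SAP. A SAP could supply a TEAE end date, but it would not make sites use one date for the visit.

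**Conclusion.** The point holds in limited form. Section 5.1 and the AE sections give different dates for the same visit, the interval from last dose to ET is unlimited, and the TEAE rule is open-ended. These facts rest on the text alone. The consequence is confined to early discontinuers whose ET visit falls after last dose: an off-drug window of g + 28 (±3) days instead of 28 (±3), plus any later SAE judged related. The probable effect is a modest over-count of TEAEs, with a window that differs between participants for administrative reasons. Its size cannot be computed from the documents; every figure beyond the 28 and ±3 days depends on assumed gaps, rates and discontinuation. It should be corrected because it affects the primary safety tables and is cheap to correct.

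**What to change.** 1. Reconcile the Final Safety Visit anchor between Section 5.1 and Sections 9.2.1, 10.4.2.1 and 2, and align 8.1.2 with the result. Which visit timing to use is for the sponsor.
2. In 10.4.2.1, define TEAEs for analysis as events with onset or worsening from the first IM011077 dose through 28 days after the last dose, the documents' own follow-up length. Either visit anchor yields collection to about that point (25 days at the earliest edge of the visit window), so this makes the tables largely insensitive to the anchor a site used.
3. Summarise or list later-onset events separately, keeping late malignancies and related SAEs visible.
4. As a minor item, reconcile the study-discontinuation wording in 7.7.4.2 with 5.1.3, 7.7.4.1 and 8.1.

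Cost: wording changes, one derived variable and one extra listing. The downside is that a few late events leave the main TEAE tables, which is why the separate display matters.

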5.1.1 Qualification and Enrollment into Study

At the end of treatment visit for the parent IBD study (ie, Studies IM011023, IM011024, and IM011127), the end of treatment procedures will be performed per protocol. Participants who successfully complete the protocol-required treatment period with an acceptable safety profile, are in clinical response or clinical remission, *and* who have no worsening on endoscopy by Simple Endoscopic Score for CD (SES-CD) [REDACTED] or Mayo endoscopic subscore ([Appendix 13](#)) from the parent study baseline (as assessed by local read) may be eligible to participate in Study

IM011077. The end of treatment visit for the parent IBD study will also be the baseline visit (Day 1) of Study IM011077.

Prior to enrollment into Study IM011077, the investigator will evaluate whether the participants remain qualified for continued long-term participation based on the inclusion and exclusion criteria listed in [Section 6](#) (Study Population).

Participants entering Study IM011077 will not be expected to complete the [REDACTED] safety follow-up period of the parent study and are expected to transition into Study IM011077 from the end of treatment visit of the parent study. If same-day transition does not occur between the parent study end of treatment and Day 1 of Study IM011077, participants must enter the study within [REDACTED] (see below for exceptions) of the end of treatment visit of the parent study. The end of treatment assessments should be repeated as indicated in [Section 2](#) (Schedule of Activities). The only exception to this [REDACTED] is when the delay is due to clinical or regulatory issues (eg, resolution or treatment for an otherwise exclusionary AE, clinical laboratory value, or delayed Institutional Review Board [IRB]/Independent Ethics Committee [IEC] approval), investigators must discuss a participant's continued participation with the BMS Medical Monitor/designee prior to enrolling the participant.

Relevant laboratory and endoscopy data, along with clinical and patient-reported outcome (PRO) assessments from the end of treatment visit in the parent study will constitute the baseline measures for Study IM011077 (see [Section 10.4.1.1](#) [Definition of Baseline] for a full description of how baseline will be derived for efficacy parameters). Depending on the timing of when a participant enters Study IM011077 (ie, visit window), these procedures may or may not be repeated at the Day 1 visit as indicated in [Section 2](#) (Schedule of Activities). The data from this visit will be entered into both the parent study and Study IM011077 databases (eg, eCRFs). Any assessments specific to Study IM011077 must be performed after the informed consent and prior to dispensation of study treatment.

